7.3 DISPOSITION OF SUBJECTS

The primary reason for screen failure will be summarized.

The number and percentage of subjects who complete study drug, prematurely discontinue study drug, and do not complete all study visits will be summarized overall for Part 1, and by treatment and overall for Part 2. In addition, the number and percentage of subjects will be summarized for each reason of discontinuation of study drug and study visits. Subjects' study completion data, including reasons for premature termination, will be listed by study part for all subjects.

The number and percentage of subjects who comprised each analysis set will be summarized for Part 1 by overall and for Part 2 by treatment and overall total for all subjects.

7.4 PROTOCOL DEVIATIONS

The significant protocol deviations will be provided in a data listing and summarized by treatment (Part 2 only) and overall total.

7.5 DEMOGRAPHIC AND BASELINE CHARACTERISTICS

Demographic and baseline characteristics will be summarized for all randomized subjects by treatment sequence (Part 2 only) and overall total. Summary statistics (N, mean, SD, median, minimum, and maximum) will be generated for continuous variables (i.e., age, height, weight, and BMI, and years of full-time education), and the number and percentage of subjects within

each category will be presented for categorical variables (i.e. gender, race, ethnicity, caffeine consumption, alcohol use, academic qualifications, and smoking status).

Demographic variables of screen failure subjects and reasons for screen failures will be summarized for all subjects who are screened but not enrolled in the study. Individual demographic characteristics, date of informed consent, any available safety data and reason for screen failure will also be presented in the data listing.

7.6 MEDICAL HISTORY AND CONCURRENT MEDICAL CONDITIONS

Medical history obtained includes determining whether the subjects has any significant conditions or diseases relevant to the disease under study that resolved at or prior to signing of informed consent. Ongoing conditions are considered concurrent medical conditions.

Medical history and concurrent medical condition verbatim reported terms will be coded using the Medical Dictionary for Regulatory Activities (MedDRA). No summaries for medical history and concurrent medical conditions will be provided. All medical history and concurrent medical conditions will be listed.

7.7 MEDICATION HISTORY AND CONCOMITANT MEDICATIONS

Medication history information obtained includes any medication relevant to eligibility criteria stopped at or within 30 days prior to signing of informed consent. Medications used from signing of informed consent through the end of study will be considered as concomitant medications.

Medication history and concomitant medications will be coded using World Health Organization Drug Dictionary. No summaries for medication history and concomitant medications will be provided. All medication history and concomitant medications data will be listed.

7.8 STUDY DRUG EXPOSURE AND COMPLIANCE

The date and time of each dose for each subject will be reported in the data listing for all subjects. Summaries of PK data will be provided by treatment. No other summary statistics for the extent of exposure to study drug or compliance calculations will be performed for this study.

7.9 EFFICACY ANALYSIS

Not applicable.

7.10 PHARMACOKINETIC ANALYSIS

7.10.1 PLASMA PHARMACOKINETIC CONCENTRATIONS

Collection of Blood Samples for Pharmacokinetic Analysis – Part 1

Analyte	Matrix	Dosing Day	Scheduled Time (hours)
TAK-071	Plasma	1	Pre-dose (within 30 minutes before TAK-071 dosing) and 0.25, 0.5, 1, 1.5, 2, 3, 4, 6, 8, 10, 12, 14, 24, 25, 26, 27, 28, 30, 32, 34, 36, 40, 48, 56, 64, 72, 96, and 168 hours post TAK-071 dose

Collection of Blood Samples for Pharmacokinetic Analysis – Part 2

Analyte	Matrix	Dosing Day	Scheduled Time (hours)
TAK-071	Plasma	1	-24 hours (predose of TAK-071) and 0 (predose of scopolamine), 1, 2, 3, 4, 6, and 10 hours postdose relative to scopolamine dosing.
Scopolamine	Plasma	1	Predose (predose of scopolamine) and 1, 2, 3, 4, 6, and 8 hours postdose relative to scopolamine dosing.
Donepezil	Plasma	1	-3 hours (predose of donepezil) and 0 (predose of scopolamine), 1, 2, 3, 4, 6, and 10 hours postdose relative to scopolamine dosing.

Note: For Part 2 time points relative to each study drug administration are as follows:

TAK-071: predose (approximately 30 minutes before dosing) and 24, 25, 26, 27, 28, 30, and 34 hours postdose relative to TAK-071 dosing;

Donepezil: predose (within 30 minutes before dosing) and 3, 4, 5, 6, 7, 9, and 13 hours postdose relative to donepezil dosing;

Scopolamine: predose (predose of scopolamine) and 1, 2, 3, 4, 6, and 8 hours postdose relative to scopolamine dosing.

The concentration of TAK-071 and donepezil will be summarized separately by treatment, as applicable, over each scheduled sampling time using descriptive statistics (including N, arithmetic mean, SD, CV%, median, minimum, maximum, geometric mean, and CV% of the geometric mean).

Individual plasma concentration data versus time will be presented similarly in data listings. Additionally, graphical plots of individual and mean plasma concentration vs time profiles will be presented for Part 1 (TAK-071) only.

No listings or summaries from the scopolamine concentration data will be presented.

7.10.2 PLASMA PHARMACOKINETIC PARAMETERS

Since Part 2 of the study was terminated early, the following parameters will only be computed for Part 1. The PK parameters of plasma TAK-071 will be determined from the concentration-time profiles for all evaluable subjects according to standard noncompartmental analysis methods. Actual sampling times, rather than scheduled sampling times, will be used in all computations involving sampling times.

The following PK parameters will be calculated for plasma concentration values of TAK-071:

Symbol/Term	Definition
Plasma	
AUC_{last}	Area under the plasma concentration-time curve from time 0 to time of last quantifiable concentration.
AUC_{∞}	Area under the plasma concentration-time curve from time 0 to infinity, as permitted by the data.
C_{max}	Maximum observed plasma concentration.
$t_{1/2z}$	Terminal disposition phase half-life.
t_{max}	Time to first occurrence of C_{max} , as permitted by the data.

Additional plasma PK parameters may be calculated if necessary, in accordance with the Clinical Pharmacology Analysis Plan.

Plasma PK parameters for TAK-071 will be listed and summarized separately by treatment. Descriptive statistics (including N, arithmetic mean, SD, CV%, median, minimum, maximum, geometric mean, and CV% of the geometric mean) will be used as appropriate. Geometric mean and CV% of the geometric mean will be reported for AUCs and C_{max} only. All subjects with a valid PK parameter estimate will be included in the summaries and analyses for that parameter.

In addition to the above, other PK analysis methodologies may be employed to further characterize the PK behavior of TAK-071 in healthy subjects, including conventional compartmental analyses and nonlinear mixed-effect modeling using TAK-071 pooled data across studies.

7.10.3 PHARMACODYNAMIC PARAMETERS

Since Part 2 was terminated early, these endpoints will not be listed or summarized.

7.11 SAFETY ANALYSIS

The safety of TAK-071 in combination with scopolamine will be assessed through AEs, clinical laboratory results, physical examination findings, ECG findings, vital signs, and suicidal assessments. All safety summary tables are presented by treatment group within Part 1 and Part 2.

7.11.1 ADVERSE EVENTS

A TEAE is defined as an adverse event or a serious adverse event (SAE) that occurs or gets worse after receiving the first dose of study drug (the dose administered on Day 1 for Part 1 and on Day 1 of Period 1 for Part 2; run-in scopolamine is considered study drug) until the Follow-up Visit/Call or Early Termination. A TEAE may also be a pretreatment adverse event or a concurrent medical condition diagnosed prior to the date of first dose of study drug that increases in severity after the start of dosing.

Adverse event verbatim reported terms will be coded by system organ class, high-level term and preferred term using MedDRA.

TEAE summary tables will include numbers and percentages of subjects experiencing at least one AE by system organ class (SOC) and preferred term (PT) and will be tabulated by treatment group within Part 1 and Part 2. TEAEs will be summarized according to the treatment most recently received prior to the onset of the event.

The following is a list of AE summary tables to be generated:

- Overview of TEAEs.
- TEAEs by SOC and PT at subject and event level.
- Subject Mappings for TEAEs.
- TEAEs by PT.
- Most Frequent TEAEs by PT.
- Most Frequent Non-Serious TEAEs by PT.
- Relationship of TEAEs to Study Drug by SOC and PT.
- Drug-Related TEAEs by SOC and PT.
- Intensity of TEAEs by SOC and PT.
- Intensity of Drug-Related TEAEs by SOC and PT.
- Pretreatment Events by SOC and PT.

If a subject has more than one AE that codes to the same PT, the subject will be counted only once for that PT. If a subject has more than one AE within an SOC category, the subject will be counted only once for that SOC. TEAEs possibly or probably related to study medication will be tabulated in the same manner. TEAEs will also be summarized by maximum intensity.

Most frequent TEAEs are defined as the AEs occurring in at least 2 subjects in any treatment (ie, Treatment A).

Data listings will be provided for all AEs (including pretreatment events for enrolled subjects), AEs leading to study drug discontinuation, SAEs, and AEs resulting in death.

7.11.2 CLINICAL LABORATORY EVALUATIONS

All samples are collected in accordance with acceptable laboratory procedures. During the treatment period, laboratory samples are taken following a minimum 8 hour overnight fast on the days stipulated in the Schedule of Study Procedures (refer to Appendix A in protocol).

For Part 1, blood samples for clinical laboratory tests (hematology, coagulation, serum chemistry, urinalysis) are collected at Screening, at Check-in (Day -1), on Days 1 through 5 (Final Visit)/ Early Termination (ET), Day 8, and at the Follow-up Visit.

For Part 2, blood samples for clinical laboratory tests (hematology, coagulation, serum chemistry, urinalysis) are collected at Screening and in each period at Check-in (Day -1), at Study Exit (on Day 3 of Period 5/ET), and Follow-up (on Day 9 [± 2] of Period 5), as appropriate.

Individual results for hematology, chemistry, and coagulation laboratory tests are evaluated against the Takeda predefined laboratory markedly abnormal value (MAV) criteria ([Appendix A](#)) using the result and criteria in SI units.

Clinical laboratory tests (hematology, chemistry, and urinalysis) will be listed. The results that meet MAV criteria will be flagged in the listing. For Part 1 only, baseline, postdose and change from Baseline to postdose laboratory data will be summarized. Baseline is defined as the last non-missing measurement prior to first dose of study drug.

The percentage of subjects who meet MAV criteria at least once postdose will be summarized by overall total for Part 1 and by treatment and overall total for Part 2..

7.11.3 VITAL SIGNS

Vital signs include body temperature (oral), respiratory rate, supine blood pressure (systolic and diastolic, resting more than 5 minutes), and pulse (beats per minute [bpm]).

All measurements are recorded on the source documents and in the eCRF.

When vital signs are scheduled at the same time as blood draws, the blood draw takes priority and vital signs are obtained within 0.5 hour before or after the scheduled blood draw.

For Part 1, vital signs (oral temperature, respiration, pulse, and blood pressure) are obtained at Screening, at Check-in (Day -1), on Days 1 through 5 (Final Visit)/ ET, Day 8, and at the Follow-up Visit (on Day 12).

For Part 2, vital signs (oral temperature, respiration, pulse, and blood pressure) are obtained at Screening and in each period at Check-in (Day -1), Day 1 (-26 hours predose), and Day 3 (period 1 to 4), Study Exit ([Day 3 of Period 5]/ ET), and Follow-up (Day 9 [± 2]) of Period 5, as appropriate.

Individual vital signs are evaluated against Takeda's predefined criteria for MAV ([Appendix B](#)). All vital signs will be listed. The results that meet MAV criteria will be flagged in the listing. Baseline, postdose and change from Baseline to postdose vital signs parameters will be summarized. Baseline is defined as the last non-missing measurement prior to first dose of study drug for subjects in Part 1. Baseline is defined as the last non-missing measurement prior to first dose of study drug in the respective treatment period for subjects in Part 2

The percentage of subjects who meet MAV criteria of vital signs at least once postdose will be summarized by overall total for Part 1 and by treatment and overall total for Part 2.

7.11.4 12-LEAD ECGs

A standard 12-lead ECG is recorded. The investigator (or a qualified observer at the investigational site) will interpret the ECG using 1 of the following categories: within normal limits, abnormal but not clinically significant (NCS), or abnormal and clinically significant (CS). The following parameters will be recorded from the subject's ECG trace: heart rate, RR interval, PR interval, QRS interval, and QTcF (QT interval with Fridericia correction method) and QTcB (QT interval with Bazett correction method) interval.

If an ECG is scheduled at the same time as blood draws or vital signs, the ECG is obtained within 0.5 hours before the scheduled blood draw/vital sign assessment. Predose ECGs may be done within 1 hour prior to dosing. If an ECG coincides with a meal, the ECG takes precedence followed by the meal.

For Part 1, a standard 12-lead ECG is recorded at Screening, Check-in (Day -1), Day 1 (predose [within 60 minutes prior to dosing]), on Days 2 through 5 (upon morning rising)/ ET, Day 8, and at the Follow-up (on Day 12[±2]).

For Part 2, a standard 12-lead ECG is recorded at Screening, and in each period at Check-in (Day -1), Day 1 (predose [within 60 minutes prior to dosing], Day 3 (Period 1 to 4), Study Exit (Day 8 of Period 5)/ ET, and Follow-up (Day 9 [±2] of Period 5), as appropriate.

Individual ECGs are evaluated against Takeda's predefined criteria for MAV ([Appendix C](#)). All ECGs will be listed. The results that meet MAV criteria will be flagged in the listing. Baseline, postdose and change from Baseline to postdose ECG parameters will be summarized. Baseline is defined as the last non-missing measurement prior to first dose of study drug for subjects in Part 1. Baseline is defined as the last non-missing measurement prior to first dose of study drug in the respective treatment period for subjects in Part 2

The percentage of subjects who meet MAV criteria of ECGs at least once postdose will be summarized by overall total.

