11. Subject has current or recent (within 6 months) gastrointestinal disease that would be expected to influence the absorption of drugs (ie, a history of malabsorption, esophageal reflux, peptic ulcer disease, erosive esophagitis, frequent [more than once per week] occurrence of heartburn, or any surgical intervention).
12. Subject has a history of cancer, except basal cell carcinoma which has been in remission for at least 5 years prior to Day 1 of Period 1.
13. Subject has a positive test result for hepatitis B surface antigen (HBsAg), hepatitis C virus (HCV) antibody at Screening or a known history of human immunodeficiency virus infection.
14. Subject has used nicotine-containing products (including but not limited to cigarettes, pipes, cigars, chewing tobacco, nicotine patch or nicotine gum) within 28 days prior to Check-in Day -1 of Period 1. Cotinine test is positive at Screening or Check-in (Day -1) of Period 1.
15. The subject has poor peripheral venous access.
16. Subject has donated or lost 450 mL or more of his blood volume (including plasmapheresis), or had a transfusion of any blood product within 30 days prior to Day 1 of Period 1.
17. The subject has a risk of suicide or suicidal ideation with intent and plan according to the investigator's clinical judgment (affirmative answer to questions 4 and 5 of the ideation section of the Columbia-Suicide Severity Rating Scale [C-SSRS]) or has made a suicide attempt in the previous 6 months.
18. The subject is a shift worker (night, late, or early resulting in irregular bed times) or has crossed or will cross more than 2 time zones within 48 hours in the period from 48 hours prior to Treatment Period 1, Day 1 until the end of Treatment Period 5.
19. The subject reports symptoms suggesting evidence of a current sleep disorder or history of sleep disorder, including but not limited to sleep apnea, heavy snoring, primary or chronic insomnia, narcolepsy or restless leg syndrome, as judged by medical history.

20. The subject has a Fridericia-corrected QT interval >450 ms or PR interval outside the range of 120 to 220 ms, confirmed on repeat testing within a maximum of 30 minutes, at Screening or Check-in.
21. Subject has abnormal Screening or Check-in (Day -1) of Period 1 laboratory values that suggest a clinically significant underlying disease, confirmed upon repeat testing.

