Appendix B Criteria for Markedly Abnormal Values for Vital Signs

Parameter	Unit	Lower Criteria	Upper Criteria
Pulse	bpm	<50	>120
Systolic blood pressure	mm Hg	<85	>180
Diastolic blood pressure	mm Hg	<50	>110
Body temperature	°C	< 35.6	>37.7

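### The postdose MAV percentages do not separate values already beyond the limit at Baseline from new ones, and Part 2 has only about 2 to 3 subjects per treatment

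*SAP*

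**What the plan says.** **Counting rule.** For vital signs, SAP 7.11.3 specifies "The percentage of subjects who meet MAV criteria of vital signs at least once postdose" and adds that it "will be summarized by overall total for Part 1 and by treatment and overall total for Part 2". SAP 7.11.2 words the laboratory rule the same way, with the same presentation. SAP 7.11.4 specifies "The percentage of subjects who meet MAV criteria of ECGs at least once postdose", but summarizes it by overall total only. The general statement in SAP 7.11 puts all safety tables by treatment group, so the two ECG instructions do not agree.

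**Baseline.** SAP 7.1.3 and 7.11.3 define it: "Baseline is defined as the last non-missing measurement prior to first dose of study drug in the respective treatment period for subjects in Part 2". It feeds the change summaries ("Baseline, postdose and change from Baseline to postdose vital signs parameters will be summarized") but not the MAV count. For laboratory data, SAP 7.11.2 restricts the change summary to Part 1. All values are listed: "The results that meet MAV criteria will be flagged in the listing".

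**Limits.** SAP Appendix B sets absolute limits only, including pulse below 50 bpm and diastolic pressure below 50 mm Hg. Appendix C sets absolute limits for heart rate (below 50 bpm) and uncorrected QT (460 ms or more). Only QTcB and QTcF have a criterion that involves change from Baseline.

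**Entry.** Protocol 7.2 item 20 excludes a man if "The subject has a Fridericia-corrected QT interval >450 ms or PR interval outside the range of 120 to 220 ms" on confirmed testing. Nothing in Protocol 7.1 to 7.3 bounds pulse, blood pressure, ECG heart rate or uncorrected QT. Item 21 excludes laboratory values only where they suggest clinically significant disease.

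**Size.** SAP 7.1 states that 12 subjects enrolled in Part 2 and none began Period 2.

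**The concern.** A postdose MAV percentage shown by treatment invites the reader to ask what happened after each treatment. As defined, it also counts what was there before. A man with a resting pulse of 46 before and after dosing has not changed, yet he is in the numerator. SAP 7.11.1 handles adverse events differently: a treatment-emergent event must be new or worse after the first dose.

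In the planned crossover this mattered less, because each completer would have contributed to all five treatment columns. With Period 1 only, each man sits in one column, so chance allocation of a single man with a pre-existing value can create or mask a difference between columns. The MAV percentages are also among the few endpoints left: SAP 5.1 and 5.3 drop the primary and exploratory endpoints, and SAP 5.2 keeps treatment-emergent adverse events, MAVs and Part 1 pharmacokinetics.

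**Working it through.** The plan states no MAV rate and no Period 1 group sizes, so it has no figure of its own to reproduce.

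**1. Can an eligible man already be beyond a limit?**

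- *Pulse and diastolic pressure.* No numeric entry limit exists. Clinical judgement of disease (Protocol 7.2 items 4 and 10) is the only barrier, and it need not exclude a healthy man with a low resting pulse.
- *Uncorrected QT.* By the Fridericia relation, QT = QTcF × (60/HR)^(1/3). Three men who pass the QTcF part of item 20:

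| QTcF (ms) | HR (bpm) | QT (ms) |
|---|---|---|
| 450 | 56 | 450 × (60/56)^(1/3) = 460.5 |
| 440 | 52 | 440 × (60/52)^(1/3) = 461.5 |
| 430 | 48 | 430 × (60/48)^(1/3) = 463.2 |

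All three meet the QT limit of 460 ms before any dose. At 50 bpm, any QTcF from 433 to 450 ms gives a QT of 460 to 478 ms.

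**2. Group sizes.** 12 subjects / 5 treatments = 2.4 on average. In SAP Table 4.a each treatment opens exactly two of the ten sequences. The block size is not stated. With assumed blocks of 10, the first ten men give 2 per treatment. The last two share a treatment with probability 1/9 = 0.11, which gives one column of 4; otherwise every column has 2 or 3 (probability 0.89). With assumed blocks of 20 or 40, columns from 0 to 4 or wider are possible.

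**3. Contribution of one pre-existing value (1/n).**

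| Table | n | Points added |
|---|---|---|
| Part 2 vital signs or laboratory, by treatment | 2 | 50.0 |
| Same | 3 | 33.3 |
| Same | 4 | 25.0 |
| Part 2 overall, including ECG under SAP 7.11.4 | 12 | 8.3 |
| Part 1 (planned size) | 6 | 16.7 |

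**4. How likely is at least one such man among 12?** The documents give no rate, so the Baseline proportion p is assumed. The chance is 1 − (1 − p)^12: 11.4% at p = 1%, 46.0% at p = 5% and 71.8% at p = 10%.

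**The case against.** **The information is already there.** For vital signs and ECGs, change from Baseline is summarized and every value is listed with flags. With 12 men, a pulse of 46 before and after dosing can be found. This stands in part. A man who does not change adds zero to a mean change but still counts in the percentage, no shift table is planned, and Part 2 laboratory data have no change summary at all.

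**Nothing is attributed to drug.** A reader might infer that a pre-existing value would be reported as a drug effect. The SAP does not support that: the percentages are descriptive, no test or causality rule is attached to MAVs, and placebo (Treatment A) has its own column. The value would only be tabulated as a postdose MAV under the treatment received.

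**The ECG case is smaller.** A reader might carry the 33 to 50 points over to the QT examples. SAP 7.11.4 gives no treatment columns, so 8.3 points of the Part 2 total is the supported figure unless the by-treatment sentence in SAP 7.11 governs. QTcF and QTcB are also largely protected, by item 20 and by the change-from-Baseline criterion.

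**The laboratory case is weaker.** Item 21 removes values that suggest significant disease, and Protocol 9.1.8 requires abnormalities found before the first dose to be documented as not clinically significant before randomization. An MAV judged not significant could still enter.

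**Removing Baseline MAVs could hide harm.** This stands. A man at 49 bpm at Baseline who falls to 38 would leave the numerator. Any postdose MAV is also the endpoint in Protocol 5.2.2, so replacing it would change a protocol-defined endpoint.

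**Small numbers are the real cause.** Any single event moves a column of 2 or 3 this far. That is true, and it is why each event should be identifiable as new or pre-existing.

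**Conclusion.** The concern holds, with limits. SAP 7.11.2 to 7.11.4 put pre-existing and new MAVs in one count, and the entry criteria admit men already beyond the pulse, diastolic pressure, heart-rate or uncorrected-QT limits. One such man adds about 33 to 50 points to a Part 2 vital-sign column, or to a laboratory column on the weaker grounds given above, and about 8 points to the Part 2 ECG total.

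The column figures assume near-even allocation, which the documents do not state, and the overall figure assumes that all 12 men are in the denominator. How often such men occur is unknown. The flaw is one of presentation in a descriptive safety table. It is worth correcting because this endpoint is one of the few that remain and the data needed are already collected.

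**What to change.** In SAP 7.11.2 to 7.11.4, keep the protocol-defined postdose percentage and split it, as n/N for each parameter and direction, into:

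- (a) criterion not met at the SAP 7.1.3 Baseline (treatment-emergent);
- (b) criterion already met at that Baseline, with each such subject's Baseline and worst postdose values shown so that worsening stays visible.

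Keep every flag in the listings. Reconcile the overall-only ECG presentation in SAP 7.11.4 with the by-treatment statement in SAP 7.11. Record the change in SAP 7.13.

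The cost is SAP wording and one extra split in the MAV tables. No new data are needed, and the endpoint in Protocol 5.2.2 is unchanged.
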